#### 4.9.3 Aim 2 Analytic Approach

**12-Month Utilization (H3):** Incremental medical costs will be estimated using standard health econometric methods. A generalized estimating equation (typically assuming a gamma distribution and log link function) will be used to estimate costs by study arm while allowing clustering by clinic and controlling for demographics and baseline clinical risk factors. The marginal effect of being assigned to an intervention clinic will provide an estimate of the incremental medical cost associated with the CP-CDS intervention. Urban and rural clinic- based eligible subjects receiving care from eligible PCPs will also be

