Several recent developments make EHR-linked Web-based point-of-care CDS for cancer preventive services feasible on a large scale for the first time: (a) over 80% of PCPs now use EHR systems, (b) we have shown in a randomized controlled trial that our EHR-linked, Web-based approach to CDS significantly improves chronic disease care in high-risk adults, (c) this CDS system requires only minor adjustments in clinic workflow and does not slow PCPs down, (d) Web-based algorithms can be easily updated and are highly scalable to both large and small healthcare delivery systems, and (e) previous cost-effectiveness analysis indicates that this approach to CDS is highly cost-effective and may be cost-saving at scale. After adapting previous work to the needs of our new clinical target, we will randomly assign 36 primary care clinics (34 clinic randomization units) to 3 groups (11 intervention clinic units in the PCP-focused group, 11 intervention clinic units in the SDMT-focused group, and 12 usual care control clinic units) with approximately 300 PCPs and more than 153,000 primary care patients. The number of clinic units to be randomized (34) is smaller than the number of clinics in the study (36) due to three small clinics being grouped together. A particular focus in our project is to compare the impact of a PCP-focused CDS workflow with a SDMT-focused CDS workflow.

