**3.3 Study Design:** Supported by CFIR and RE-AIM frameworks, the implementation process for CP-CDS has four phases: a) initial organizational engagement; b) adopting and piloting the CP-CDS with Essentia Health (EH) PCPs and patients; c) a cluster-randomized controlled trial with 3 arms in 36 EH primary care clinics (34 randomized clinic units), and d) evaluation of the implementation process and outcomes. Because three small clinics were randomized together, there are 34 randomized units in this study. Five randomization schemes were developed using random numbers and 1:1:1 allocation to the three study arms. The randomization scheme selected was pre-determined to be the first of five schemes (blind to clinic allocation) with adequate balance on factors of clinic urbanicity, % of patients who were current smokers, % of patients under 30, total number of patient visits per clinic, % of patients with Medicaid, breast cancer screening rate, geographic region, count of patient with serious mental illness, count of patient with pre-diabetes, colorectal cancer screening rate, access to low-dose lung screening, and participation in a community wellness initiative. Quantification of study arm balance was not based on a priori cut-offs but on subjective assessment of balance by the study team.

The two arms were randomly assigned to either the PCP-focused intervention (CP-CDS) or SDMT-focused intervention (CP-CDS + SDMT). The 12-usual care (UC) clinics for the Cardiovascular Wizard studies will continue as control clinics with the CP-CDS (Figure 1) in a 1:1:1 allocation. Because three small clinics were randomized together, there are 34 randomized units in this study.

[figure not shown]
Eligible patients will be allocated to the study arm assigned to their clinic at their index visit.

**3.4 Study Sites:** This study will be conducted at 36 Essentia Health (EH) primary care clinics in North Dakota, Minnesota, and Wisconsin. Leaders at EH are fully committed to the project, as indicated in letters of support from Drs. [name] and [name]. These 36 clinics have used the EpiCare® EHR since 2004 and have, on average, 12 PCPs and 3,996 eligible patients per clinic (range, 318–11,823). Ten participating EH clinics are classified as rural, 7 as micro, 8 as small towns, and 9 as urban by the RUCA2-UR coding system.

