## 4.9 Analysis Plan

### 4.9.1 Aim 1 Analytic Approach

Hypotheses 1 & 2 in Aim 1 posit that patients seen at clinics with the SDMT-focused or PCP-focused cancer screening CDS will be more likely than patients seen at UC clinics without the CDS to have appropriate screening for breast, cervical, and colon cancer (H1), and a full course of three HPV vaccinations (H2) within 12 months of an index visit. Because clinics are the unit of randomization and the outcome varies at the level of the patient, generalized linear mixed-model regression with a logit link and binomial error distribution will be used to test the effect of the interventions. The general form of the analytic model for H1 & H2 is:

$$\text{Dependent Variable}_{kji} = \gamma_{00} + \gamma_{100}\text{SDMT\_CDS}_k + \gamma_{200}\text{PCP\_CDS}_k + \gamma_{001}\text{SEX}_i + [\nu_{k00} + u_{kji} + e_{kji}]$$

The dependent variable in each model is a binary indicator of appropriate screening (H1) or complete course of HPV vaccination (H2). The dependent variable is predicted by the two fixed-effect terms representing the study arm contrast (SDMT\_CDS and PCP\_CDS). Patient sex is included as a fixed effect because screening rates for H1 and vaccination rates for H2 are likely to be different. We will screen patient characteristics to determine

whether they differ across study arm and include patient covariates in the model when they are unbalanced by treatment arm. Random terms are included for clinic ( $v_{k00}$ ), provider ( $u_{kj0}$ ), and patient ( $e_{kii}$ ). The provider random term will be removed if the provider intra-cluster correlation (ICC) is less than 0.005. A significant treatment group effect ( $P<0.025$ ) and positive and significant parameters for the treatment group terms  $\gamma_{100}$  and  $\gamma_{200}$  for each hypothesis will support the H1 & H2 predictions that clinics with CDS interventions are more effective than clinics without them for increasing cancer screening and HPV vaccination rates. This model will include patient sex and patient variables unbalanced by study arm as well as the indicated random effects. Treatment group heterogeneity by sex will be assessed by including interaction terms between patient sex and the two study arm indicators.

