**Table 3. Anticipated pattern of effects for H2 (receipt of 3 HPV vaccinations)**

UC	20% (30% F, 10% M)
PCP CDS	33% (45% F, 20% M)
SDMT CDS	40% (55% F, 25% M)

compared. The estimates assume that the CP-CDS is implemented in a large health plan with an EHR capable of exporting data to Web-based clinical algorithms. Implementation in settings without this capability would likely incur additional costs.

**12-Month Diagnostic and Billing Codes (H4):** Similar to costs, a generalized estimating equation with a time  $\times$  study group interaction term will be used to estimate use rates of diagnostic and billing codes for cancer preventive services or the encounter billing level by study arm while allowing for clustering by clinic and controlling for demographics and baseline clinical risk factors. The marginal effect of being assigned to an intervention clinic will provide an estimate of the incremental effect associated with the intervention. All statistical comparisons will be 2-sided. P-values of less than .05 will be considered statistically significant.

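### H3 and H4 rest on a GEE with 34 clusters and no small-sample correction; under the usual GEE default, H3 type I error per contrast would be about 7-12%, not 5%

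*Combined protocol and SAP*

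**What the plan says.** Section 4.9.3 sets out both Aim 2 tests. For H3 the model is described as "A generalized estimating equation (typically assuming a gamma distribution and log link function"), and it "will be used to estimate costs by study arm while allowing clustering by clinic". For H4 a GEE with a time-by-group interaction estimates code use and billing level "by study arm while allowing for clustering by clinic and controlling for demographics and baseline clinical risk factors". The decision rule closes the H4 paragraph but is worded generally: "All statistical comparisons will be 2-sided" and "P-values of less than .05 will be considered statistically significant".

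The number of clusters is given elsewhere. Section 1.3 plans to "randomly assign 36 primary care clinics (34 clinic randomization units) to 3 groups", with 11, 11 and 12 units per arm. Section 3.3 explains the count: "Because three small clinics were randomized together, there are 34 randomized units in this study". Section 3.4 gives a mean of 3,996 eligible patients per clinic, with a range of 318 to 11,823.

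Nowhere does the plan state the variance estimator, the working correlation, the reference distribution, the degrees of freedom, or any permutation or cluster-level alternative for Aim 2.

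**The concern.** The sandwich variance of a GEE is justified as the number of clusters grows. With few clusters it is biased downward, and a normal reference ignores the uncertainty of the variance estimate. Both errors make intervals too short. A large number of patients does not help, because the relevant count is clusters: 34 in all and 23 in each comparison with usual care. Very unequal clinic sizes make the bias worse when clinics are weighted by their patients.

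H3 and H4 predict higher costs and more code use in the two intervention arms. An anti-conservative test would declare such differences too often. Because the inferential method is left open, it could also be chosen after the data are seen.

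**Working it through.** **Inputs from the documents.** 34 units, 12/11/11 (sections 1.3 and 3.3); two-sided .05 (4.9.3); clinic sizes with mean 3,996 and range 318 to 11,823 (3.4); ICC 0.005 to 0.02, given only for the Aim 1 endpoints (4.9.2); 38,053 service calls, to be cut to the first per patient for cost (Figure A.3).

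**Assumptions.** Clinic-size CV of 0, 0.60, 0.76 and 0.85 (sizes drawn lognormal and clipped to the stated range); patient cost CV of 2; between-clinic SD on the log scale of 0.15 or 0.30. The implied ICC is SD²/(SD² + CV²): 0.0225/4.0225 = 0.0056 and 0.09/4.09 = 0.0220, close to the Aim 1 range.

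**Step 1: the plan's own cluster arithmetic.** Aim 2 has no power calculation, so the only stated figure to test is the 5% level. As a check on the cluster inputs, N/(1 + (m−1)·ICC) with 10 clinics per arm reproduces the Aim 1 effective sample sizes.
- H1: N = 3,133 + 11,088 = 14,221 and m = 1,422.1. At ICC 0.005, 14,221/8.11 = 1,754 (stated 1,754). At 0.02, 14,221/29.42 = 483 (stated 484).
- H2: N = 7,092 and m = 709.2. This gives 7,092/4.541 = 1,562 and 7,092/15.164 = 468 (stated 1,562 and 468).

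**Step 2: level without simulation.** With n equally weighted clusters per arm, the uncorrected sandwich variance is (n−1)/n times the unbiased one. The z test therefore rejects when |t| on 2n−2 df exceeds 1.96·√((n−1)/n).
- n = 11: cut-off 1.869 on 20 df, level 7.6%.
- n = 12: cut-off 1.877 on 22 df, level 7.4%.

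This needs no ICC or size assumption. It treats cluster means as roughly normal.

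**Step 3: simulation under the null.** Log-link arm means, 60,000 runs per row and SD. Weights are m (independence) or m/(1 + (m−1)·ICC) (exchangeable). The level per contrast with usual care is shown in %, with the two values for log-SD 0.15 and 0.30.

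| Size CV | Weights | Uncorrected, z | Uncorrected, t(31) | Mancl-DeRouen, t(31) |
|---|---|---|---|---|
| 0 | exchangeable | 7.4 / 8.1 | 6.3 / 6.9 | 4.4 / 4.8 |
| 0.60 | exchangeable | 7.8 / 8.1 | 6.7 / 7.0 | 4.7 / 4.9 |
| 0.76 | exchangeable | 7.8 / 8.0 | 6.7 / 6.9 | 4.5 / 4.9 |
| 0.60 | independence | 9.6 / 10.1 | 8.4 / 8.9 | 5.1 / 5.4 |
| 0.76 | independence | 10.9 / 11.4 | 9.7 / 10.1 | 5.4 / 5.6 |
| 0.85 | independence | 11.5 / 12.3 | 10.3 / 11.0 | 5.6 / 5.9 |

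Over all settings run, including identity-scale ones, equal sizes or exchangeable weights gave 7.2-8.1%. A t reference alone does not repair the test. The Kauermann-Carroll correction with t(31) gave 5.3-5.6% with equal or exchangeable weights, but 6.6-7.7% with independence weights and unequal clinics. Mancl-DeRouen with t(31) stayed at about 4.3-5.9%.

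**Step 4: sensitivity.** With 36 clinics taken as 12 per arm, the uncorrected z test gives 7.8% (exchangeable) and 10.8% (independence). Raising the total to 34 × 3,996 = 135,864 patients gives 11.1% in the independence setting that gave 10.9% (CV 0.76, log-SD 0.15), so more patients do not help.

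**Step 5: two contrasts with usual care.** The chance of at least one false positive is about 14-21%. Two independent tests that each held 5% would give 1 − 0.95² = 9.75%.

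**The case against.** The strongest reply is that the plan is silent rather than wrong. It does not say that the sandwich variance is uncorrected or that the reference is normal, and it points to standard econometric methods through citations that cannot be consulted here. This stands. A reader might infer that the test as stated has a false-positive rate of 7-12%. The documents do not support that: the rate is what the usual default would give.

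A reader might also attach the same rate to H4. The simulated model has arms only, without time or covariates, and H4 concerns code rates and billing levels under a time-by-group interaction. The cluster limit carries over; the number does not.

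A third tempting extension is to H1 and H2, where "Random terms are included for clinic" as well as for provider and patient in a mixed model. Section 4.9.1 does not say that arm terms are tested with z. Its 0.025 threshold attaches to the overall arm effect, which section 4.8 codes with two degrees of freedom, and support also requires positive and significant arm terms. A rate worked out for a single z test at 0.025 is not the error rate of that rule. In a null simulation with a chi-square reference, the overall test alone ran at 3.6%, and the overall test plus both arm terms at 0.2-0.4%. No H1/H2 error rate is claimed here.

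The upper range does rest on assumptions. The plan gives no ICC for costs. The stated size range counts eligible patients rather than cost-analysis records, and independence weights are not specified. The lower range survives all of this, because Step 2 uses neither ICC nor size variation.

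Finally, requiring exchangeable weights could change what is estimated. At the stated extremes one clinic is 37 times larger than another (11,823/318), yet exchangeable weights would give it only about 1.15 times the weight at ICC 0.02 and 1.6 times at 0.005. Aim 2 takes the health-system perspective, where a patient-weighted average may be intended. This also stands, and it shapes the fix.

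**Conclusion.** The concern holds as a gap in specification with a predictable consequence. H3 and H4 use a GEE at two-sided .05 on 34 units, 23 per contrast with usual care, and no small-sample correction is named. An analyst who runs the H3 model with an uncorrected sandwich variance and a normal reference would have a type I error per contrast of about 7-8% with equal clinic sizes or exchangeable weights. With independence weights it would be about 10-12%, given an assumed clinic-size CV of 0.6 to 0.85, since the plan reports only a mean and range. For H4 the same limit applies, with its size not quantified. Covariate adjustment was not simulated for either hypothesis. These are Aim 2 tests and the remedy is cheap, so the change should be made, although the screening and vaccination tests of Aim 1 do not depend on it.

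**What to change.** In section 4.9.3, for both H3 and H4:
- State that the cluster is the randomized unit (34 units), so that the three clinics randomized together count as one.
- Name a bias-corrected sandwich variance. Mancl-DeRouen is preferred, because Kauermann-Carroll remains above 5% under independence weights with unequal clinics.
- Refer tests and intervals to t or F on 34 − 3 = 31 degrees of freedom, fewer if clinic-level covariates are added.
- Say whether the target is a patient-weighted or a clinic-weighted effect, and fix the working correlation in advance to match, rather than adopting exchangeable by default.

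This needs no new data. It costs a few sentences, a software setting and one decision about the estimand. Intervals become slightly wider.

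The H4 model can be checked by repeating the null simulation with its time-by-group term and the planned covariates.

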**Hypothesis 3 (H3).** After controlling for demographics and baseline clinical risk factors, eligible study subjects will have significantly different overall healthcare costs during the 12 months after the index visit by study arm, with PCP-focused and SDMT-focused arms higher than the UC arm.

**Hypothesis 4 (H4).** After controlling for demographics and baseline clinical risk factors, eligible study subjects will have significantly different frequencies of diagnostic codes related to cancer prevention services and billing levels in the 12 months after the index visit by study arm, with PCP-focused and SDMT-focused arms higher than the UC arm.

**Specific Aim 3.** Describe critical facilitators and barriers for the CP-CDS implementation process, outcomes, and future dissemination strategies using a mixed-methods approach supported by the CFIR and RE-AIM conceptual frameworks.

Results of this pioneering project will: (a) lead to improved delivery of personalized, evidence-based primary and secondary cancer preventive services, helping achieve Healthy People 2020 goals; (b) advance our understanding of how best to integrate effective personalized cancer preventive CDS into primary care workflows; and (c) guide effective dissemination and implementation of similar EHR-linked, Web-based, personalized CDS systems to other rural primary care clinics and delivery systems.

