Intervention costs include CDS implementation and maintenance, training, and incentives but exclude intervention research and development costs. Medical care costs include costs of all medical services-including laboratory, physician services, and screening tests-incurred in the 12-month post-index date period by participants in each study group, as indicated by EH billing and clinical encounter data. Described in detail in the Section 4.9.3 below, we will use relative value units (RVUs) and diagnosis-related groups (DRG) to calculate inpatient and outpatient costs for patients randomly assigned to each study group and standard accounting methods to measure the cost of the CP-CDS intervention. Emergency visits and hospitalizations may be too infrequent in the study sample to accurately predict a population-wide impact of the study interventions. If there were no intervention impact on these utilization components during the study period, including their costs would substantially increase variance in the cost data without adding to the accuracy of the cost assessment. Therefore, we will first assess whether there is a differential impact between CP-CDS and usual care on use of these services and will include their costs only if a difference is observed. Reliance on EH billing records for measuring medical care use may miss costs incurred in other health systems; however, this opportunity is expected to be equal across randomized study arms, and cross-system medical utilization is expected to be relatively limited in the primarily rural study population.

While market prices generally are a good estimate of the costs for medical services, the paid amount in this claims system is specific to HealthPartners at a particular time and may provide a biased view of costs between pre- and post-intervention periods. To address this, we will use Total Care Relative Resource Values™ (TCRRVs), which are a nationally standardized set of measures that have been endorsed by the National Quality Forum and are derived from Centers for Medicare and Medicaid Services (CMS) relative value units (RVUs). TCRRVs extend CMS RVU measures to include utilization categories, such as laboratory services and medications, which do not have CMS RVU weights. Specifically, TCCRVs defined during the midpoint of patient accrual and follow-up (e.g., 2019) will be used to convert claims to represent U.S. dollars.

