- Some variables are static (e.g., provider type, patient ethnicity)
- The two smoking-related endpoints examine occurrence of an event over 12-month time period following the index date
- Cost variables include information from the index visit as well as utilization over a 12-month time period

Fields to extract and return:

For Sample 1 (H1, H2, Lung, Smoking):

- Variables and definitions listed in data dictionary in the “[name] variables” tab
- For each record in Index 7\_5 mo stacked, please attach the following variables: study\_id, patient\_id, ethnicity, insurance status, RUCA code of clinic at index visit, provider type, provider dept, provider age, provider gender (if readily available), referral to smoking cessation counseling
- Attaching prescription orders might go as follows: In a separate file, for all records in “index 7\_5 mo stacked”, provide all prescription orders from 8/1/18 – 3/16/20 with separate fields for NDC code (if available), prescription order date, generic name, brand name

For Sample 1 ([name] utilization analysis):

- See “Cost” tabs in data dictionary for this aim
- There are four tabs (yellow) requesting data elements

For Sample 2 (HPV sample: patients age 9-17 due for HPV vaccination)

- Variables and definitions listed in “CPW data dictionary” in the “HPV” tab

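### The H3 cost model names no pre-index cost covariate, and the plan does not make clear whether pre-index cost is extracted at all; with 11, 11 and 12 units this gives up precision that is cheap to recover.

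*Combined protocol and SAP*

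**What the plan says.** **Hypothesis.** Hypothesis 3 in the Specific Aims predicts that "eligible study subjects will have significantly different overall healthcare costs during the 12 months after the index visit by study arm".

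**Model.** Section 4.9.3 fits a generalized estimating equation, typically gamma with a log link, "allowing clustering by clinic and controlling for demographics and baseline clinical risk factors". The estimate comes from the arm term: "The marginal effect of being assigned to an intervention clinic will provide an estimate of the incremental medical cost associated with the CP-CDS intervention". The H3 paragraph contains no time term and names no prior cost or prior utilization.

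**Outcome.** Section 4.7 counts medical costs "incurred in the 12-month post-index date period by participants in each study group, as indicated by EH billing and clinical encounter data".

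**Extract.** The time-frame list in Appendix A, Figure A.3 says: "Cost variables include information from the index visit as well as utilization over a 12-month time period". The fields are set in a separate data dictionary, of which the appendix says only: "There are four tabs (yellow) requesting data elements". Those tabs are not reproduced.

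**Text pointing to a pre-period.** Section 4.7 argues for standardized prices because amounts paid "may provide a biased view of costs between pre- and post-intervention periods". The H4 paragraph of section 4.9.3 presents its model as resembling the cost model and gives it a time-by-arm interaction, which needs data from before the intervention.

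**The concern.** H3 compares arms through a small number of clinic units: 11 PCP-focused, 11 SDMT-focused and 12 usual care (section 1.3). Clinics differ widely, with 318 to 11,823 eligible patients each and settings from rural to urban (section 3.4). With so few units, variation in cost between clinics limits the precision of the contrast however many patients each clinic supplies.

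A clinic that was expensive before the trial may well be expensive during it. Measuring that earlier cost and adjusting for it removes the predictable part of the variation. The plan does not say that it will do this, and no cost measure is among the factors on which arm balance was inspected (section 3.3). At stake is whether Aim 2 can separate an intervention effect on cost from chance differences between clinics. The documents give no power, standard deviation or intra-cluster correlation for H3, so nothing in them shows how precise the planned model would be.

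**Working it through.** **A figure to reproduce.** There is none for H3. As a check on how the plan treats clustering, the Aim 1 effective sample sizes (section 4.9.2) follow from n / (1 + (m − 1) × ICC) with 10 clinics per arm:

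- H1: n = 3,133 + 11,088 = 14,221 and m = 1,422.1, giving 483.3 at ICC 0.02 and 1,754.5 at ICC 0.005 (stated 484 to 1754).
- H2: n = 7,092 and m = 709.2, giving 467.7 and 1,561.8 (stated 468 to 1562).

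These agree to within one patient. Clustering is thus quantified for Aim 1 but not for H3.

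**Does the plan contain a pre-index cost?**

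| Place | What it supports |
|---|---|
| Specific Aims, H3 | Outcome after index; adjustment for demographic and clinical factors |
| 4.7, cost definition | Outcome after index |
| 4.9.3, H3 model | No cost history, no time term |
| Figure A.3, time frame | Index visit plus a 12-month period, direction not stated; the smoking line just above it does specify after index |
| 4.7, pricing argument | Mentions a pre-period |
| 4.9.3, H4 model | Time-by-arm term, described as like the cost model |
| Appendix A, office visits | Period undefined, not a cost, not tied to H3 |

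The first three rows agree with one another. The fourth most naturally follows them but does not say so. The next two pull the other way without specifying anything for H3.

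**Size (illustration).** Two inputs are assumptions because the documents do not give them: the between-clinic coefficient of variation (CV) of cost left after the planned covariates, taken as 0.05 to 0.30, and the partial clinic-level correlation r between pre- and post-index cost given those covariates, taken as 0.5 to 0.9. Patient-level variance is ignored and normal quantiles are used.

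1. SE of the log cost ratio, 11 versus 12 units: sqrt(ln(1 + CV²)) × sqrt(1/11 + 1/12), where the second factor is 0.4174.
2. Chance range with no true effect: exp(±1.96 × SE).
3. Ratio detectable with 80% power at two-sided 0.05: exp((1.960 + 0.842) × SE).
4. With prior cost in the model, SE is multiplied by sqrt(1 − r²): sqrt(0.75) = 0.87, sqrt(0.51) = 0.71, sqrt(0.19) = 0.44.

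| CV | SE | 95% chance range | Detectable ratio, no prior cost | r = 0.5 | r = 0.7 | r = 0.9 |
|---|---|---|---|---|---|---|
| 0.05 | 0.021 | 0.96 to 1.04 | 1.06 | 1.05 | 1.04 | 1.03 |
| 0.10 | 0.042 | 0.92 to 1.09 | 1.12 | 1.11 | 1.09 | 1.05 |
| 0.20 | 0.083 | 0.85 to 1.18 | 1.26 | 1.22 | 1.18 | 1.11 |
| 0.30 | 0.123 | 0.79 to 1.27 | 1.41 | 1.35 | 1.28 | 1.16 |

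Worked line: at CV 0.20, sqrt(ln 1.04) = 0.198, and 0.198 × 0.4174 = 0.0827. Then exp(2.802 × 0.0827) = 1.26. With r = 0.7 the SE is 0.0590 and the ratio is 1.18.

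**The case against.** **The extract may already hold prior cost.** A reader might infer that only the index visit and the following 12 months are extracted. The documents do not establish that. The time-frame line gives no direction, the cost tabs cannot be seen, and defining an outcome after index does not show that earlier cost was not pulled. If H3 were meant to carry the time-by-arm term written for H4, stable clinic differences would drop out and the concern would largely disappear. This stands as a limit on what can be claimed. It does not rescue the plan as written, because the H3 paragraph has no such term and the pre-period wording in section 4.7 concerns pricing.

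**The differences do not remain whole.** A reader might also infer that all earlier clinic cost differences pass into the estimate. The planned covariates remove some. The balance factors in section 3.3, though none is a cost, include visit volume, Medicaid share, urbanicity and region, which plausibly track cost. This stands.

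**This is not bias.** Under randomization the remainder is chance variation, which clustering by clinic is meant to carry into the interval. This stands too, with one reservation. Section 3.3 describes a 1:1:1 randomization to three arms, but also says that two arms were randomly assigned while the usual-care clinics of earlier cardiovascular studies continue as controls. If those clinics were not re-randomized, earlier cost differences could be systematic.

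**The percentages flatter the gain.** Applied to the simple correlation, sqrt(1 − r²) would compare against a model with no covariates at all. The relevant r is the partial one, probably smaller. The cost quantity itself is also unsettled, since section 4.7 includes emergency and hospital costs only if their use differs between arms. The figures are therefore best cases.

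**Conclusion.** The point holds as a matter of precision and specification. The H3 model names no pre-index cost, and the plan is inconsistent about whether a pre-index cost period exists. With 11, 11 and 12 units, unexplained clinic cost differences stay partly in the contrast as chance imbalance and wider intervals. Whether bias is also possible depends on how the usual-care clinics were allocated, which the documents do not settle.

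A partial clinic-level correlation of 0.5, 0.7 or 0.9 would reduce interval width to at best about 87%, 71% or 44% of that under the planned model. These figures rest on an assumed correlation and ignore patient-level variance; the detectable ratios also rest on an assumed clinic CV. They show what a baseline cost term could recover. They do not show an error in any stated figure, and leaving the term out does not invalidate the H3 test.

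**What to change.** 1. State whether cost for the 12 months before index is extracted. If not, extend the date range of the existing request, using the same EH billing source, the same TCRRV pricing and the same service components as the outcome.
2. Add the patient's prior-year cost to the H3 model on the log scale, with a flag for no history and a stated rule for zero cost. The unit's mean prior-year cost may be added as an optional second term.
3. Report the model without prior cost as a sensitivity analysis.
4. Align the cost definition and pricing text in section 4.7, the H3 and H4 models in section 4.9.3, and the time frame in Figure A.3, so that all say the same about a pre-period and about whether any time-by-arm term applies to H3.
5. Clarify in section 3.3 whether the usual-care clinics were randomized in this trial.

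The cost is a longer extract window and one or two more covariates. Patients new to the system have no prior year, which is why the flag is needed. Items 4 and 5 are changes of text only.
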